**The entire study will last about 12-15 weeks.**

**E. Describe the plans for data analysis. If applicable, include statistical considerations and justification for subject population and planned enrollment numbers.**

**We will use paired t-tests or Wilcoxon Signed-rank tests (nonparametric) to examine differences between pre and post-intervention scores for the two groups. Between-group differences, variability, and effect size in outcome measures will be used to project sample size for future trials. Our analytical strategy for future trials is to estimate difference between groups in change over repeated measures (i.e. "group-by-time interaction"). We will use Pearson correlation to examine association between physical functioning and executive functioning, and between ADL/IADL performance and executive functioning.**

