#### **Follow-up Surveys and Assessments**

Twelve weeks after beginning the study, all participants will complete the same surveys and assessments completed during the beginning of the study. These surveys and assessments will be completed in the same order and using the same format as at the beginning of the study. Participants in the treatment group we will also complete a brief satisfaction survey.

**In addition, we will also record blood pressure and HBA1C readings from participants' medical records AFTER we have obtained consent from participants. For participants in the treatment group, we will use readings from their last visit with the PCP before the intervention and closest visit with the PCP after the intervention. For participants in the control group, we will use the information that is available in their medical records from the last available record before the date of completing the baseline surveys and assessments, and the next available record approximately 10 weeks after the date that they complete the baseline surveys and assessments.**

**Two occupational therapists will also be involved in the study and will provide the aforementioned intervention sessions to all patient participants. Some of these sessions might be monitored (observed in real-time) by the PI or a research assistant as part of fidelity monitoring**

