## VIII. Research Subject Population

**A.** Indicate the anticipated subject enrollment number (This number cannot be exceeded without prior IRB review and approval via an amendment): **75**

**B.** Indicate which populations below are the PRIMARY FOCUS of this research. Please refer to the [UIC HSPP policies](#) regarding the incidental enrolment of select vulnerable populations (i.e., decisionally impaired, prisoners, etc.).

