**UIC**

Initial Review Application: Social, Behavioral, and Educational Research, Version 5.2  
*student records) and upload with this application packet*

Decisionally-Impaired - *Complete Appendix V and upload with this application packet*

Economically and/or Educationally Disadvantaged

Vulnerable to Coercion or Undue Influence

Other: specify

**C.** If including economically and/or educationally disadvantaged subjects, subjects vulnerable to coercion or undue influence, UIC Employees, and/or other populations that may be considered vulnerable, provide a rationale for their inclusion and what additional safeguards, if any, are in place to protect their rights and welfare:

**Two UI Health clinicians will be included in the study as the lead interventionists. They will provide data about the treatment sessions, which is necessary to monitor the fidelity of the experimental intervention. Specifically, the PI or a research assistant will attend and observe randomly selected treatment sessions and will complete a fidelity monitoring checklist based on their observations of the clinician's delivery of the session (uploaded). Clinicians will also be asked to complete case notes for each treatment session. The case notes template is embedded in the intervention manual.**

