**D. Eligibility Criteria**

1. Provide specific details regarding the following:
  - a. Inclusion Criteria: **For patient participants:**
    - Age 55 years or over
    - Primary diagnosis of one or more of the following: diabetes ,heart disease
    - Evaluated as experiencing or being at risk of functional decline OR self-identified need for support with chronic disease management and functional health
  - b. Exclusion Criteria: **For patient participants:**
    - Unable to participate in study activities due to time or other constraints
    - Current/past diagnosis of stroke or dementia, or other neurological disorders
    - Receiving pharmacological treatment for cognition
      - Participation in other clinical trials involving a rehabilitation/functional healthmanagement component
    - Non-English speaking
    - Residing in a long-term care institution
    - Compromised decision-making capacity (score >8 on SOMCT) - - Short Orientation Memory Concentration Test (SOMCT) will be used during the screening process to ensure the participant is eligible for the study. A score of 0-8 on this test indicates normal to minimal impairment. Any one with a score>8 will be considered ineligible.
    - Not an active patient at the study clinic (two years or more since last appointment)
2. Explain how and by whom potential subjects will be assessed to determine their eligibility for the research: **A trained research assistant and graduate student in occupational therapy will assess potential subjects to determine eligibility using a screening questionnaire administered over the phone**
3. Explain how initial eligibility will be documented (upload any screening documents): **For patient participants: We have developed an eligibility screening form (attached) to ascertain eligibility of potential subjects. The screening form will include a standardized assessments for assessing risk**

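### The planned Pearson correlations are not adjusted for age, so they cannot show whether function and executive functioning are associated beyond shared ageing

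*Combined protocol and SAP*

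**What the plan says.** The whole association plan is one sentence in Section VI.E: "We will use Pearson correlation to examine association between physical functioning and executive functioning, and between ADL/IADL performance and executive functioning". It names no covariate, visit or test level, and no other section supplies them. Section XII.A mentions splitting the data by arm and by diagnosis and running more complex analyses in SAS, but it describes no adjusted association model.

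Three other places bear on the point.

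- Section VIII.D.1.a sets the age criterion as "Age 55 years or over", with no upper bound.
- Section VI.C rests the intervention on preventing physical and cognitive decline that goes with ageing and chronic disease. In Section VI.D, the first treatment session covers the effect of age and chronic disease on physical functioning.
- The measures are taken twice. Under the follow-up heading in VI.D, "all participants will complete the same surveys and assessments completed during the beginning of the study". Randomisation comes after the baseline assessments.

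Section VIII.A caps enrolment at 75.

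**The concern.** Where two measures both worsen with age and the sample spans a wide age range, they correlate even if nothing links them at a given age. By the protocol's own account, ageing affects both physical and cognitive function.

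The background in VI.A–B argues that subtle difficulty with daily activities goes with early cognitive change and can help to identify patients at risk. A reader of the results will naturally take a correlation between ADL/IADL performance and executive functioning as bearing on that argument. The crude coefficient mixes two things: a link between the domains among people of the same age, and the fact that older participants tend to do worse on both. As planned, the report would contain nothing to tell these apart.

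What is at stake is how an exploratory result is interpreted. The pre/post comparisons and the sample-size projection for future trials do not depend on it.

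**Working it through.** The documents give no target correlation, alpha or power for this analysis, so there is no stated figure to reproduce.

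**Inputs**

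- From the documents: n = 75 (VIII.A, an enrolment ceiling); age 55 or over (VIII.D); Pearson correlation with no covariate (VI.E).
- Assumed: two-sided 5% level; each measure correlates with age at a = 0.2, 0.3, 0.4 or 0.5 in absolute value; linear relations; no association between the measures once age is held fixed.

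**Step 1. Correlation induced by age.** If the partial correlation given age is zero, then r(X,Y) = r(X,age) × r(Y,age) = a². This gives 0.2² = 0.04, 0.3² = 0.09, 0.4² = 0.16 and 0.5² = 0.25.

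**Step 2. Chance that the crude test is significant.** At n = 75 the critical |r| is 0.227. By Fisher's z, with Φ the standard normal distribution function, m = atanh(r) × √(n − 3) and P = Φ(m − 1.96) + Φ(−m − 1.96). Here √72 = 8.485. For a = 0.3, m = 0.0902 × 8.485 = 0.766, so P = Φ(−1.194) + Φ(−2.726) = 0.116 + 0.003 = 0.119. A simulation of 20,000 trials per row checks the approximation and adds the partial correlation.

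| Correlation of each measure with age | Induced r | Crude test significant, Fisher z | Crude test significant, simulated | Age-adjusted test significant, simulated |
|---|---|---|---|---|
| 0.2 | 0.04 | 6.3% | 6.6% | 5.3% |
| 0.3 | 0.09 | 11.9% | 12.1% | 5.2% |
| 0.4 | 0.16 | 27.8% | 27.7% | 5.2% |
| 0.5 | 0.25 | 58.2% | 58.6% | 5.0% |

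With 60 participants the simulated crude figures are about 6%, 11%, 23% and 50%, so moderate attrition does not change the picture.

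**Step 3. What adjustment does to a borderline result.** The partial correlation is (r − a²)/(1− a²) when both measures correlate with age at a. Take an observed crude r at the critical value, 0.227:

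- a = 0.2: 0.187/0.96 = 0.195
- a = 0.3: 0.137/0.91 = 0.151
- a = 0.4: 0.067/0.84 = 0.080
- a = 0.5: −0.023/0.75 = −0.031

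The same crude value can therefore mean a modest association beyond age or none at all.

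**Step 4. Price in precision.** The 95% half-width on Fisher's z scale is 1.96/√72 = 0.231 for the crude coefficient and 1.96/√71 = 0.233 for the partial one.

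**The case against.** The strongest reply is that Pearson's r is not wrong for what it estimates. If age induces a correlation of 0.25, a marginal correlation of 0.25 really exists, and 58% is the chance of detecting it. For flagging at-risk patients, one use that the background proposes for ADL/IADL performance, the crude association is informative. This stands. The percentages are errors only if the result is read as an association beyond age, which is why the crude value should stay in the report.

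It is also fair that VI.E sets no test level, that this is a pilot, and that the assumed correlations with age have no source in the documents. The exclusions in VIII.D (dementia, stroke, other neurological disorders, SOMCT above 8) may narrow the range of executive functioning and weaken its link with age. At 0.2 the effect is negligible. The documents also do not say whether any score is already age-standardised, which would shrink the induced part.

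A reader might infer three stronger points that the documents do not support.

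- *That baseline and follow-up records will be pooled, giving false significance.* Two assessments per person exist, but no section proposes pooling them. The unnamed visit is a missing detail.
- *That this correlation is the plan's only test of its premise.* The premise is that functional deficits come before cognitive impairment, and the background supports it from literature. VI.E does not present the correlation as a test of it, and a single-visit correlation, adjusted or not, could not establish order in time.
- *That a rank-based method is required because VI.E offers "paired t-tests or Wilcoxon Signed-rank tests (nonparametric") for the pre/post scores.* No distributional problem is shown for the correlations, so ranks are optional.

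**Conclusion.** The point holds as a cheap improvement to an exploratory analysis. The documents tie ageing to both physical and cognitive decline, set no upper age limit, and plan only a crude correlation, so the result as planned cannot show whether the domains are associated beyond age.

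The effect is small if the measures correlate with age at 0.2 (induced r 0.04, significant in about 7% of trials) and large at 0.5 (induced r 0.25, about 58%). These figures rest on 75 analysed participants, a two-sided 5% level, equal correlations with age for both measures, and no age-independent association. All but the ceiling of 75 are assumptions. The 75 may also include the two clinician participants described in VIII.C, and no attrition is allowed for.

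**What to change.** In VI.E, state that the correlations use baseline scores, one record per participant, with both arms together. Baseline precedes randomisation, so treatment cannot contribute to the association and combining the arms is harmless. Report the partial correlation adjusted for age in years, with a 95% CI, beside the crude Pearson value and its 95% CI. Say in one clause that the crude value describes marginal association and the adjusted value describes association beyond age. A rank-based version may be added but is not needed.

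First confirm that the demographic survey records age in years. The protocol gives an age threshold for eligibility and mentions the survey, but does not list its items.

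The cost is about two sentences, one degree of freedom and, usually, a smaller adjusted estimate. No new visit or assessment is needed.

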**F. Is this is a clinical trial?**

No – *Skip to section VII*  
 Yes - Is the research required to be registered on <http://clinicaltrials.gov>? For more information, refer to the UIC HSPP policy [Clinical Trials Registration](#)  
 No  
 Yes – Include the required language within the informed consent document.

---

## **VII. Research Records**

**A. Indicate the type(s) of data being collected and/or recorded (check all that apply):**

Interviews/Questionnaires

Audio recordings

Video recordings

Photographs

School/Student records

Internet research data

Lab, pathology and/or radiology results

University of Illinois Hospital & Health System medical records – University of Illinois Hospital & Health System medical records (only HBA1c and

Systolic/Diastolic blood pressure readings from last visit with PCP before the

intervention and closest visit with the PCP after the intervention – patients will NOT be asked to make an appointment just for the study. For participants in the control group, we will use the information that is available in their medical records from the

Initial Review Application: Social, Behavioral, and Educational Research, Version 5.2  
 last available record before the date that they completed the baseline surveys and assessments, and the next available record approximately 10 weeks after the date that they complete the baseline surveys and assessments. For participants in both groups these data will be abstracted AFTER consent is obtained.

Physician/clinic/hospital medical records from sources outside of UI Health System  
 Psychotherapy Notes

Billing records

Data previously collected for research purposes

Data containing no health information

Study-generated health information

Biological specimens

X Other. Describe: **Performance-based observations by a clinician**

**No audio/video recordings will be collected during the course of the study**

**B.** Will any of the following be banked or stored for future (planned or unplanned) analysis **beyond the scope of the current research proposal?** If the following will be used and/or destroyed prior to the closure of the research, they are not considered to be stored; therefore, please answer "No".

- biological samples or specimens
- identifiable data,
- coded data where a master list to the codes exists

No Study assessments are only intended to generate data that will help monitor intervention and/or test study hypotheses. These data should not be considered health information.

Yes – Complete [Appendix D](#) and upload with this application packet.

**Note:** A plan for securely storing the data must be submitted for IRB review and approval if identifiable and/or coded data will be retained after the research has been completed. Development of a separate data/tissue repository/bank research protocol is required if the investigator will be retaining data from multiple proposals.

## VIII. Research Subject Population

**A.** Indicate the anticipated subject enrollment number (This number cannot be exceeded without prior IRB review and approval via an amendment): **75**

**B.** Indicate which populations below are the PRIMARY FOCUS of this research. Please refer to the [UIC HSPP policies](#) regarding the incidental enrolment of select vulnerable populations (i.e., decisionally impaired, prisoners, etc.).

**Check all that apply**

- Adults (18 years of age and older)
- Minors (17 years of age and younger) – Complete [Appendix B](#) (required regardless of primary or incidental enrollment) and upload with this application packet
- Pregnant Women, Neonates, Fetuses/Fetal Tissue – Complete [Appendix U](#) and upload with this application packet
- Prisoners – Complete [Appendix C](#) and upload with this application packet - Please note that certain types of research with prisoners approvable under the federal regulations may not be allowed under Illinois state law including, but not limited to, biomedical research.
- UIC Employees
- UIC Psychology Student Subject Pool -
  - Complete [Appendix S](#) and a debriefing document and upload with this application packet;
  - Complete and upload [Appendix B](#) if the research will involve Pool subjects who are minors. If minors will be excluded, then a scientific justification must be provided under item VIII.D.1.b, below.
- UIC Management Study Pool - Complete [Appendix S](#) and a debriefing document and upload with this application packet
- Students - Complete [Appendix S](#) (required only if the research involves classroom activities and/or

**UIC**

Initial Review Application: Social, Behavioral, and Educational Research, Version 5.2  
*student records) and upload with this application packet*

Decisionally-Impaired - *Complete Appendix V and upload with this application packet*

Economically and/or Educationally Disadvantaged

Vulnerable to Coercion or Undue Influence

Other: specify

**C.** If including economically and/or educationally disadvantaged subjects, subjects vulnerable to coercion or undue influence, UIC Employees, and/or other populations that may be considered vulnerable, provide a rationale for their inclusion and what additional safeguards, if any, are in place to protect their rights and welfare:

**Two UI Health clinicians will be included in the study as the lead interventionists. They will provide data about the treatment sessions, which is necessary to monitor the fidelity of the experimental intervention. Specifically, the PI or a research assistant will attend and observe randomly selected treatment sessions and will complete a fidelity monitoring checklist based on their observations of the clinician's delivery of the session (uploaded). Clinicians will also be asked to complete case notes for each treatment session. The case notes template is embedded in the intervention manual.**

**D. Eligibility Criteria**

1. Provide specific details regarding the following:
  - a. Inclusion Criteria: **For patient participants:**
    - Age 55 years or over
    - Primary diagnosis of one or more of the following: diabetes ,heart disease
    - Evaluated as experiencing or being at risk of functional decline OR self-identified need for support with chronic disease management and functional health
  - b. Exclusion Criteria: **For patient participants:**
    - Unable to participate in study activities due to time or other constraints
    - Current/past diagnosis of stroke or dementia, or other neurological disorders
    - Receiving pharmacological treatment for cognition
      - Participation in other clinical trials involving a rehabilitation/functional healthmanagement component
    - Non-English speaking
    - Residing in a long-term care institution
    - Compromised decision-making capacity (score >8 on SOMCT) - - Short Orientation Memory Concentration Test (SOMCT) will be used during the screening process to ensure the participant is eligible for the study. A score of 0-8 on this test indicates normal to minimal impairment. Any one with a score>8 will be considered ineligible.
    - Not an active patient at the study clinic (two years or more since last appointment)
2. Explain how and by whom potential subjects will be assessed to determine their eligibility for the research: **A trained research assistant and graduate student in occupational therapy will assess potential subjects to determine eligibility using a screening questionnaire administered over the phone**
3. Explain how initial eligibility will be documented (upload any screening documents): **For patient participants: We have developed an eligibility screening form (attached) to ascertain eligibility of potential subjects. The screening form will include a standardized assessments for assessing risk**

Initial Review Application: Social, Behavioral, and Educational Research, Version 5.2 of functional decline. Functional decline will be assessed using the Brief Risk Identification of Geriatric Health Tool (BRIGHT). Subjects will be flagged as being at risk of functional decline if they get a score of  $>=3$  on the 11 item BRIGHT. The entire screening procedure will be completed by a trained research assistant. We will maintain an Excel spreadsheet to document eligibility. The spreadsheet will be anonymized and subjects will only be identified by a serial number. For provider participants: We will not be documenting eligibility for clinicians.

4. Explain how subjects will be monitored during the course of the research to ensure that they still meet the eligibility criteria and how their continuing eligibility will be documented:

**For patient participants:** Participants in the intervention group (occupational therapy) will be continuously monitored by the occupational therapist who will administer the experimental intervention. The occupational therapist will monitor patients for any

worsening in cognitive functioning. Being in close contact with patients, she will also be aware of changes in residential situation (e.g. move to a nursing home) and enrollment in other studies that might render participants no longer eligible for this study. Participants in the control group will also be closely monitored by a research assistant through weekly phonecalls to monitor for changes in cognitive functioning, living arrangement (i.e. relocation to nursing home), and enrollment in other studies.

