Initial Review Application: Social, Behavioral, and Educational Research, Version 5.2 the U of I Endocrinology Clinic and the U of I Family Medicine Center. Individuals thus identified will be sent an email (provided their email address is available in the EHR) by the study PI introducing the study and notifying them that a member of our research team might contact them in the next couple of weeks. Physicians with healthinformatics capability who volunteer to run an EMR search to identify eligible individuals from their existing patient caseload will have the option to send a bulk message to eligible individuals using the patient portal. A script has been created for this purpose and will include the flyer for the study as an attachment. The patient portal (labelled MyChart within Epic) is typically used by physicians to communicate with patients – no changes will be made to the portal for this study. This means that we will not need a study build within EPIC. Regardless we have completed the Epic Study Build Request to adhere with institutional procedures. The research assistant will then contact individuals identified through EMRs (in the order that they appear on the EMR list) by phone and screen them for the study's inclusion criteria. Individuals who meet inclusion criteria will be invited to enroll in the study. At this time, we will not be using the UI Health Research Registry or The New Normal for this study.

C. Explain the proposed measures to minimize the possibility of coercion or undue influence on potential subjects, particularly for subjects identified in VIII.B. as being vulnerable (for example: *how will you maximize the subject's autonomous decision-making; what if the investigator is also the participant's healthcare provider, what if the participant is enrolled in a class the investigator is teaching, what if an employer/employee relationship exists*).

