### 3. Data Security

a. Describe how all types of data as selected above will be secured.

i.  Indirectly with a code linked to the identity of the subject.

Describe the coding method, specify who will have access to the code/master key, indicate where the key is stored, and explain how it will be protected against unauthorized access: **Participants who enroll in the study will be assigned a numeric code in the outcome database in RedCap i.e. outcome data from REDCap will be identified by a code. The master list including the participants' names, contact information, and corresponding numeric codes will be stored separately from the research data. The master list will be saved as a Microsoft Excel spreadsheet on the secure network server of the College of Applied Health Sciences. The file will be password protected and only the PI, [name] and key research personnel, will have access to the password. Hard copies of permission flyers completed by participants who are screened eligible and agree to be in the study will be stored in locked filing cabinets in the PI's locked research lab. Only the PI, [name] and key research personnel, will have access to the cabinet.**

PHI collected post enrollment and POST CONSENT will include the following variables – BP and HbA1c reading [for treatment group participants – at last visit with PCP before the intervention and closest visit with the PCP after the intervention. For control group participants - last time tested before completing the baseline surveys and assessments, and the next available record approximately 10 weeks.] These data will be stored in the RedCap outcome database where subjects will be identified by a code. Note that dates of readings will not be recorded. We will record these variables as 'preBP', 'postBP', 'preglucose' and 'postglucose'. After data collections is completed the coded outcomes data with identifiers removed will be exported from RedCap as a CSV or SPSS file. The coded dataset without identifiers will be stored on a lab computer at [name], which is part of the network server of the College of Applied Health Sciences.

ii.  x Directly, personal or private identifiers (identifiable elements) are maintained with the data.

Justify the inclusion of direct subject identifiers, and indicate who will have access to the data:

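### Pre blood pressure and HbA1c readings have no maximum age and their dates are not kept, so change from before enrolment can enter the pre/post comparison unseen

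*Combined protocol and SAP*

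**What the plan says.** All references are to the combined protocol and SAP.

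- **Pre and post readings, treatment arm** (Section VI.D, Follow-up Surveys and Assessments): "we will use readings from their last visit with the PCP before the intervention and closest visit with the PCP after the intervention".
- **Pre reading, control arm** (same place): "last available record before the date of completing the baseline surveys and assessments".
- **Post reading, control arm** (same place): "the next available record approximately 10 weeks after the date that they complete the baseline surveys and assessments".
- **No refreshing visit** (Section VII.A): "patients will NOT be asked to make an appointment just for the study".
- **Dates** (Section XII.B.3, Data Security): "Note that dates of readings will not be recorded". Each marker is stored in the outcome database as one pre and one post variable.
- **Nearest limit on recency** (Section VIII.D.1.b, exclusion criteria): "Not an active patient at the study clinic (two years or more since last appointment".
- **A recruitment route not tied to a current visit** (Section IX.B, item 4): "The research assistant will then contact individuals identified through EMRs (in the order that they appear on the EMR list) by phone".

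The abstraction rule is repeated in Sections VII.A, XII.B.1 and XII.B.3. None of these places gives a maximum age for the pre reading. The analysis in Section VI.E is a paired t-test or Wilcoxon signed-rank test of pre against post for the two groups. Between-group differences, variability and effect sizes are to be used to size later trials.

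**The concern.** A paired test takes the pre value as the patient's state at entry. Here it is the state at some earlier routine contact, and the plan neither limits nor records how much earlier. Any change in treatment or disease between that contact and enrolment is then part of the measured difference. Three things are at stake:

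- The within-arm tests may show change that happened before the study began.
- The between-group contrast gains noise, because patients differ in how old their pre value is.
- The change-score variability passed to a future trial reflects an unknown mixture of interval lengths.

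Without dates or reading ages in the dataset, the analyst cannot tell whether any of this occurred, and cannot adjust for it.

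**Working it through.** The plan gives no power, alpha or sample-size figure for these markers, so there is no stated number to reproduce. What can be computed is the share of elapsed time that lies before the study.

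**Formula.** Share = a / (a + s + d), where *a* is the age of the pre reading at baseline, *s* the study time and *d* the delay of the post reading beyond the end of study time, all in weeks.

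**Inputs.**
- *s* = 10 (control-arm post anchor), 12 (follow-up, Section VI.D) or 15 (upper end of the 12 to 15 week duration given just before Section VI.E).
- *a* is not given. It is varied from 12 to 104 weeks.
- *d* is not given. It is taken as 0, or as 13 by assumption.

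**Post reading at the end of study time (d = 0).**

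| a | s = 15 | s = 12 | s = 10 |
|---|---|---|---|
| 12 | 12/27 = 44% | 12/24 = 50% | 12/22 = 55% |
| 26 | 26/41 = 63% | 26/38 = 68% | 26/36 = 72% |
| 52 | 52/67 = 78% | 52/64 = 81% | 52/62 = 84% |
| 104 | 104/119 = 87% | 104/116 = 90% | 104/114 = 91% |

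With d = 0 the share passes one half exactly when a exceeds s, that is, at about 10 to 15 weeks.

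**Late post reading (d = 13).** At a = 26 the share is 26/54 = 48% to 26/49 = 53%. At a = 104 it is 104/132 = 79% to 104/127 = 82%.

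**An ordinary schedule.** Suppose routine visits are evenly spaced every 26 weeks. The average pre reading is then 13 weeks old. Since the post reading also comes from a routine visit, it falls on average 13 weeks after week 12. At these averages the share is 13/(13 + 12 + 13) = 13/38 = 34%. Fixing the post reading at exactly week 12 would give 13/25 = 52%, but that does not fit a plan in which no appointment is made for the study.

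**Does the two-year criterion cap a?** No. It counts time since an appointment at the study clinic, and an appointment need not produce a reading. The treatment-arm rule looks to PCP visits, while one recruiting clinic is an endocrinology clinic (Section IX.A). Some providers see patients only by phone or video (Section IX.B, item 2). The 104-week row is therefore an illustration and not a bound.

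**What drift alone could do to a within-arm test (illustration).** Assume equal allocation of the enrolment ceiling of 75 (Section VIII.A), so about 37 per arm, and a two-sided 5% paired t-test. The documents state neither the allocation ratio nor alpha. If the mean change before the study is δ standard deviations of the change score and the intervention does nothing, the test statistic is noncentral t with 36 degrees of freedom and noncentrality δ√37. For δ = 0.1, 0.2, 0.3 and 0.5 the rejection rate is 9%, 22%, 43% and 84%. The values of δ are assumed, since nothing in the documents indicates which applies.

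**The case against.** The strongest reply has four parts.

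- **Time is not drift.** A reader might infer from the table that the recorded change is mostly pre-study drift. The documents do not support that. The percentages are shares of calendar time, and a stable patient can have an old reading and little net change. This objection stands.
- **Randomisation protects the comparison.** Participants are randomised after baseline (Section VI.D), so pre-study drift and recruitment route are balanced in expectation. A reader might infer a biased treatment contrast, but staleness alone does not produce one. What remains is noise in that contrast and misattribution in the within-arm tests. The arms do use differently worded anchors, so equal reading ages are not assured and ought to be checked.
- **The markers are peripheral.** They are introduced as additional data, are not named as primary or secondary outcomes, and are not mentioned in Section VI.E. Nothing says that a future trial would be sized on them. This limits the weight of the point.
- **Using records as found is a deliberate choice, and a strict cut-off has its own cost.** Setting old values to missing would remove mainly patients without recent visits, so noise would be exchanged for selective loss. Nor would limits of 3 or 6 months do much: 13/25 = 52% and 26/38 = 68% of the time could still precede the study. This argues against discarding readings, but not against recording their age.

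A reader might also infer that patients recruited at a clinic visit have fresh baselines and those from the EMR list do not. The remote and endocrinology routes do not guarantee a recent PCP reading, so the documents do not establish that split.

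**Conclusion.** The point holds in a limited form. The plan, followed exactly, admits pre readings of any age and keeps nothing from which that age could be recovered in the study dataset. The within-arm paired tests for these markers, assuming Section VI.E is meant to cover them, cannot be read as change over the intervention. The between-group summary and its variability carry extra noise of unknown amount.

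No size can be put on the effect in units of blood pressure or HbA1c, because that needs a drift rate and a distribution of reading ages that the documents do not give. The share of elapsed time depends on when both readings fall, and ranges from about a third under an assumed 26-week visit schedule to around 90% for a two-year-old reading and a prompt post reading. The consequence is confined to two unranked, record-based measures in a pilot, so this is a minor improvement.

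**What to change.** In Section XII.B.3, replace the statement that dates are not kept, and align Sections VI.D, VII.A and XII.B.1 with the new text:

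1. For each marker, in both arms, record the whole number of weeks from the pre reading to baseline and from baseline to the post reading, as coded numbers without calendar dates. Let the first be negative where a treatment-arm pre reading falls between baseline and the start of the intervention.
2. In Section VI.E, report the distribution of both intervals by arm.
3. State that the within-arm paired test for these markers is not interpreted as change over the intervention.
4. Keep older readings in the main between-group summary. Add a sensitivity analysis restricted to pre readings no older than a pre-specified limit, the same in both arms and near the study interval of about 10 to 15 weeks. State how many pairs remain.

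The cost is two coded fields per marker and edits to the abstraction and analysis text. Participants have no extra visit, and storing week counts keeps calendar dates out of the dataset. The sensitivity subset will be smaller and possibly selected towards patients who attend more often, and the report should say so. The number of usable pairs and the spread of reading ages are in themselves useful feasibility results for a pilot.
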